9.1.2. Summary Measure

For each of these parameters, except tmax, tmin, and tlag, the following summary statistics will be calculated for each active treatment group: median, maximum, minimum, arithmetic mean, standard deviation, coefficient of variation on arithmetic mean, geometric mean, coefficient of variation on geometric mean, 95% confidence interval for the geometric mean and standard deviation of logarithmically transformed data. For tmax, tmin, and tlag, median, maximum, minimum, arithmetic mean and standard deviation will be calculated.

9.1.3. Population of Interest

The primary pharmacokinetic analyses will be based on the Pharmacokinetic population, unless otherwise specified.

9.1.4. Statistical Analyses / Methods

Details of the planned displays are provided in [Appendix 11](#): List of Data Displays and will be based on GSK Data Standards and statistical principles.

Unless otherwise specified, endpoints / variables defined in Section [9.1.1](#) will be summarised using descriptive statistics, graphically presented (where appropriate) and listed.

CONFIDENTIAL

208132

9.1.4.1. Dose proportionality**9.1.4.1.1. Statistical Methodology Specification**

The following pharmacokinetic statistical analyses will only be performed if sufficient data is available (i.e. if participants have well defined plasma profiles). The statistical model will be fitted for Part 1 and Part 2 combined data.

Endpoint / Variables

 Plasma primary PK endpoints on log₁₀ scale include Day 1: AUC(0-24), C_{max} and C₂₄; Day 8/9/10 in Part 1 and Day 7 in Part 2: AUC(0-τ) and C_{max} and C_τ.
Model Specification

 To assess the dose proportionality of plasma GSK3640254, PK parameters on log₁₀ scale from Day1 [AUC(0-24) , C_{max} and C₂₄] and Day 8/9/10 for Part 1 or Day 7 for Part 2 [AUC(0-τ), C_{max} and C_τ] will be assessed using a power model if multiple dose levels are assessed. The power model will be fitted by restricted maximum likelihood (REML) using SAS Proc Mixed. A fixed effects power model will be used. The mean slope will be estimated from the power model with the corresponding 90% CI, separately for Day 1 and Day 8/9/10 for Part 1 or Day 7 for Part 2. Additionally, if power model does not show dose proportionality, dose proportionality may be assessed by pair-wise analysis of variance(ANOVA) using the SAS Mixed model procedure. A reference dose of 10 mg will be used and the other doses would be treated as test dose. PK parameters will be normalized to the reference dose and then log-transformed prior to the analysis. Point estimates and 90% confidence intervals for AUC and C_{max} will be reported to 4 decimal places with no rounding. An example of SAS code is also included here for the ANOVA approach.
Model Checking & Diagnostics

 Model assumptions will be applied, but appropriate adjustments may be made based on the data. The Kenward and Roger method for approximating the denominator degrees of freedom and correcting for bias in the estimated variance-covariance of the fixed effects will be used. Akaike's Information Criteria (AIC) will be used to assist with the selection of covariance structure.
Model Results Presentation

Statistical analysis for dose proportionality from Day 1 [AUC(0-24) , C_{max} and C₂₄] and Day 8/9/10 in Part 1 and Day 7 in Part 2 [AUC(0-τ), C_{max} and C_τ] will be presented in tabular format, respectively. The linear model will be used to provide a slope, intercept and a 90% CI of the slope.
 
Example SAS Code for power model:
 <pre>PROC MIXED; MODEL LNPKEPARAM=LNDOSE /SOLUTION CL ALPHA=0.1; ODS OUTPUT SOLUTIONF=SOLUTION1(RENAME=(ESTIMATE=EST STDERR=SE)); RUN;</pre> 
Example SAS Code for ANOVA model:
 <pre>ODS output solutionf=stat; Proc Mixed; class treatment; /* treatments are different dose groups */ model logdnPKvar = treatment/dfm=kr; lsmeans treatment; /* assuming one ref and four test treatments */ estimate 'test1 vs ref' treatment -1 1 0 0 0 /cl alpha=0.1; estimate 'test2 vs ref' treatment -1 0 1 0 0/cl alpha=0.1; run;</pre>

CONFIDENTIAL

208132

9.1.4.2. Steady State**9.1.4.2.1. Statistical Methodology Specification**

The following pharmacokinetic statistical analyses will only be performed if sufficient data is available (i.e. if participants have well defined plasma profiles). Statistical model will be fitted for Part 1 and Part 2 respectively.

Endpoint / Variables

 Plasma primary PK endpoints include Visit 2 to visit 6 Pre-dose concentrations C_0 and visit 5 C_{τ}
Model Specification

 To assess the achievement of steady state with the pre-dose concentrations between Visit 2~6 for each treatment. A linear mixed model using Day as fixed effects and subject as a random effect on the ln-transformed pre-dose values will be performed evaluating whether steady state was achieved using Helmert transformation approach. The comparison will begin with Visit 2~6 then Visit 3~6, etc. The estimate and 90% CI of the slope for the day will be presented for the comparison(s).
Model Checking & Diagnostics

 Model assumptions will be applied, but appropriate adjustments may be made based on the data. Statistical analysis of steady state will be analyze using Helmert transformation approach.
Model Results Presentation

Code will be separated for Part 1 and Part 2 due to the different study design of the two parts. Example SAS Code for Part 1: PROC MIXED; BY TREATMENT; WHERE (DAY IN (2,3,4,5,6,7,8,9,10,11)); CLASS SUBJECT; MODEL LOGCTAU = DAY/CL ALPHA=0.1 SOLUTION; RANDOM INTERCEPT/SUBJECT=SUBJECT TYPE=UN; RUN;

10. PHARMACODYNAMIC ANALYSES

10.1. Primary Pharmacodynamic Analyses

Relationships between dose and PD measures (maximum change (in Day 1 to Day 8) in log₁₀ plasma HIV-1 RNA from baseline) will be explored with an Emax and linear models. Part 1 and Part 2 doses combined in the model fitting. Model selection will be based on Akaike Information Criteria (AIC) value, where model with the lowest AIC value will be considered the best model.

10.1.1. Endpoint / Variables

- Log₁₀ Maximum change from baseline to Day 8 and change from baseline to Day 8 in plasma HIV-1 RNA

10.1.2. Summary Measure

- Parameter estimates for Emax, ED50 and variance along with their standard error, and 95% CI

10.1.3. Population of Interest

The primary pharmacodynamics analyses will be based on the PP population, unless otherwise specified.

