10.3.2.2. Efficacy Analyses

Both the PP and ITT Populations will be used for all efficacy analyses if there are dropouts. Plasma HIV-1 RNA max change and change from baseline during the study will be calculated for each participant and on each assessment visit/day.

Plasma HIV-1 RNA will be listed by treatment, participant, and assessment visit/day and summarized by treatment and assessment visit along with change from baseline.

Plots of mean and median plasma HIV-1 RNA actual and change from baseline data will be generated by treatment and assessment visit.

- Plasma HIV-1 RNA change from baseline to the nadir (maximum change from baseline) will be calculated for each participant and summarized by treatment.

Together, the data from Parts 1 and 2 will investigate the complete dose-exposure-response curve and the impact of lower doses/exposures on potential development of resistance.

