4. ANALYSIS POPULATIONS

Population	Definition / Criteria	Analyses Evaluated
Screened	
 All participants who were screened for eligibility 	
 Study Population
Enrolled	
 All participants who passed screening and entered the study. Note screening failures (who never passed screening even if rescreened) and participants screened but never enrolled into the study (Reserve, Not Used) are excluded from the Enrolled population as they did not enter the study. 	
 Study Population
Randomized	
 All participants who were randomly assigned to treatment in the study. This population will be based on the treatment the participant was randomized to. 	
 Study Population
Safety	
 All randomized participants who received at least one dose of study treatment. This population will be analysed based on the treatment the participant actually received. 	
 Study Population Safety
Intent-To-Treat Exposed (ITT)	
 All randomized participants who meet the study criteria and are enrolled into the study with documented evidence of having received at least one dose of treatment and at least one post-baseline HIV-1 RNA measurement. This will be the primary population for the final efficacy analysis for all active treatment groups. This population will be based on the treatment the participant was randomized to. 	
 Efficacy
Per-Protocol (PP)	
 all participants who meet study criteria and are enrolled into the study with documented evidence of having received all doses and all post-baseline HIV-1 RNA measurement. Protocol deviations that would exclude participants from the PP population are defined in Section 4.1 (Protocol Deviations) and Appendix 1: Protocol Deviation Management and Definitions for Per Protocol Population. The PP set will not be analysed if no participants drop out of ITT population. 	
 Efficacy

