Pharmacokinetic (PK)	
 The PK Population will include all participants who receive GSK3640254 and undergo plasma PK sampling during the study. Participants for whom a plasma PK sample is obtained and assayed will be included in the listing of plasma GSK3640254 concentration-time data. Results from samples collected from a participant with emesis occurring within 2 hours of the dose will not be considered as evaluable. 	
 PK
Pharmacokinetic/ Pharmacodynamic (PK/PD)	
 Participants who meet criteria for Per-Protocol and Pharmacokinetic Population analysis sets and who undergo PD sampling during the study. 	
 Pharmacokinetic/ Pharmacodynamic

Refer to [Appendix 11](#): List of Data Displays which details the population used for each display.

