11.1.2. Population of Interest

The primary pharmacodynamics analyses will be based on the PK/PD population, unless otherwise specified. Part 1 Day 9~11 HIV RNA are excluded to fulfil the same dosing days and be used in one statistical model.

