13. APPENDICES

13.1. Appendix 1: Protocol Deviation Management and Definitions for Per Protocol Population

13.1.1. Exclusions from Per Protocol Population

A participant meeting any of the following criteria will be excluded from the Per Protocol population:

Number	Exclusion Description
1	Participant who deviated from any inclusion/exclusion criteria
2	Participant who did not receive correct treatment which the participant was randomized to
3	Participant who have missed at least one dose of GSK3640254
4	Participant who did not have Visit 6 HIV-RNA measurement
5	Not withdrawn after meeting the following stopping criteria 
 • Liver chemistry stopping criteria • QTc stopping criteria • Stopping criteria based on Laboratory Abnormality and Adverse Event
6	Informed Consent 
 • Study-specific assessments conducted prior to obtaining proper consent.
7	Study visits performed out of window 
 • Consecutive participant study visits performed out of window • Multiple study visits performed out of window by various Participants (Trending)
8	Incorrect study treatment 
 • Unresolved IP accountability discrepancy • IP storage guidelines not followed • IP incorrectly administered • IP accountability not done
9	Lack of PI oversight
10	Participant Used prohibited medication
11	Participant became pregnant while on study
12	Safety assessments not performed when clinically relevant 
 • Central safety lab samples not collected and/or not properly sent to Q2 when clinically relevant

CONFIDENTIAL

208132

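### The dose-response and exposure-response models use HIV-1 RNA only through Day 8, but their Per-Protocol-based sets can drop participants for later samples or doses the models do not use

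*SAP*

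**What the plan says.** **Which set each model uses.** SAP Section 10.1.3 puts dose-response in PP: "The primary pharmacodynamics analyses will be based on the PP population, unless otherwise specified". The display list follows (Table 5.1, Figure 5.1, Listing 55). For exposure-response, SAP Section 11.1.2 says: "The primary pharmacodynamics analyses will be based on the PK/PD population, unless otherwise specified". Table 6.1, Figures 6.1 and 6.2 and Listing 56 use that set, which SAP Section 4 defines as "Participants who meet criteria for Per-Protocol and Pharmacokinetic Population analysis sets and who undergo PD sampling during the study". It is therefore contained in PP. No ITT version of either model is listed.

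**How PP is defined.** SAP Section 4 asks for "documented evidence of having received all doses and all post-baseline HIV-1 RNA measurement", and protocol Section 10.2 uses the same criterion. Section 4 then sends the reader to Appendix 1 (Section 13.1.1) for the deviations that exclude. On RNA, criterion 4 there reads "Participant who did not have Visit 6 HIV-RNA measurement". Criterion 3 excludes anyone who missed a dose. Visit 6 is Day 11 in Part 1 and Day 8 in Part 2 (SAP Section 7.1.1).

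**Which RNA data the models use.** SAP Section 10.1.4 limits the dose-response fit to visits through Day 8 in both parts. SAP Section 11.1.2 removes Part 1 RNA from Days 9 to 11 so that the two parts cover the same dosing days.

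**The protocol's rule for efficacy.** Protocol Section 10.3.2.2: "Both the PP and ITT Populations will be used for all efficacy analyses if there are dropouts".

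**The concern.** The models were cut at Day 8 so that 10-day and 7-day dosing could share one curve, but the analysis set was not cut with them. A participant can supply everything a model needs and still be removed for something that happens afterwards. That loses information in arms of 6 and makes inclusion depend on events after the outcome was measured. The two statements of the PP rule also classify some participants differently, so two programmers could build different sets from the same SAP. Protocol Section 3.1 says the study's data will be used to select Phase 2b doses, and these two models describe how response varies with dose and exposure.

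**Working it through.** **1. Sample size.** Part 1: 6 + 6 + 2 = 14. Part 2: 3 × 6 + 2 = 20. The total is 34, as stated in protocol Section 5.2. On active drug: 12 + 18 = 30.

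**2. RNA samples required and used** (protocol Section 2.2):

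| | Part 1 | Part 2 |
|---|---|---|
| Post-baseline RNA samples | 8 (Visits 2–9) | 6 (Visits 2–7) |
| Counted as inside the Day 8 window | 4 (Visits 2–5) | 5 (Visits 2–6) |
| After the window | 4 (Visits 6–9, Day 11 onward) | 1 (Visit 7, Day 10–12) |

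Part 1 has no fixed Day 8 visit, because Visit 5 is Day 8, 9 or 10. The table counts Visit 5 as inside the window. When it falls on Day 9 or 10, a fifth Part 1 sample lies outside. In Part 2, cART starts on Day 8 after the blood draw, so the Visit 7 sample is taken on cART.

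**3. Four participants, classified under each rule:**

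| Participant | Section 4 | Appendix 1 | Data the models use |
|---|---|---|---|
| Part 1, misses only Visit 8 | out | in | complete |
| Part 1, misses only Day 11 | out | out | complete |
| Part 2, misses only Visit 7 | out | in | complete |
| Part 1, all RNA, misses the Day 9 dose | out | out | Table 5.1 unaffected; Table 6.1 depends on the Visit 5 day |

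The first and third rows show the two rules disagreeing. The second shows that adopting Appendix 1 alone would not repair Part 1.

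On the fourth row, blood is drawn before dosing (protocol Section 2.2, footnote 1). A dose missed on Days 8 to 10 therefore cannot affect RNA measured through Day 8. Table 6.1 differs because its PK parameters come from Visit 5 (SAP Sections 9.1.1.2 and 11.1.3). If Visit 5 is Day 9 or 10, a missed Day 9 dose alters the modelled exposure.

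**4. Expected loss due only to a later sample.** The documents give no missing rate. Assume each sample is missed independently with probability p, and let q = 1 − p.

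Under Section 4: 12 × (q⁴ − q⁸) + 18 × (q⁵ − q⁶).

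- p = 3%: 12 × (0.8853 − 0.7837) + 18 × (0.8587 − 0.8330) = 1.2 + 0.5 = 1.7
- p = 5%: 12 × (0.8145 − 0.6634) + 18 × (0.7738 − 0.7351) = 1.8 + 0.7 = 2.5

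Under Appendix 1 criterion 4, only the Part 1 Day 11 sample matters: 12 × q⁴ × (1 − q).

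- p = 3%: 12 × 0.8853 × 0.03 = 0.3
- p = 5%: 12 × 0.8145 × 0.05 = 0.5

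Over a wider range under Section 4, the expected loss is 0.6 at p = 1% and 3.8 at p = 10%.

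**5. Effect on the pooled fit.** Use the information matrix of the two-parameter Emax model in SAP Section 10.1.4.1 with doses 10, 40, 80, 140 and 200 mg and six participants per dose. SD 0.4 is from protocol Section 10.1.1; Emax 2 log10 and ED50 5 to 20 mg are assumptions. Losing one of six at 10 mg changes the standard error of ED50 as follows:

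- ED50 = 5: 2.200 to 2.365 (+7.5%)
- ED50 = 10: 3.755 to 4.011 (+6.8%)
- ED50 = 20: 7.634 to 8.019 (+5.0%)

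**The case against.** **PP is a defensible set for these models.** Protocol Section 10.3.3.1 places PK/PD and dose-PD modelling under secondary analyses, treats them as exploratory and leaves detail to the analysis plan. The primary antiviral endpoint is already analysed in ITT. Modelling response against assigned dose in participants who took every dose is reasonable; an ITT fit enters someone with missed doses at the full assigned dose. This stands. A reader might infer that ITT must be the primary set for Tables 5.1 and 6.1, but the documents do not require it. They do support an ITT fit alongside: the response is HIV-1 RNA change, and protocol Section 10.3.2.2, which calls for both sets, also says the two parts together will investigate the dose-exposure-response curve.

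**The two PP statements can be read as cumulative**, since Section 4 refers to Appendix 1. Criterion 4 is then merely redundant. That reading gives the stricter rule, so the post-Day-8 exclusions remain.

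**Part 1 losses may be smaller.** SAP Section 3.1 reports in the past tense that the interim followed the Part 1 Day 12 visit, which suggests Visits 6 and 7 were largely attended. With only Visits 8 and 9 at risk in Part 1, the loss is 12 × q⁴ × (1 − q²) + 18 × (q⁵ − q⁶): 1.1 at 3% and 1.6 at 5%. This is a fair reduction, though it does not reach zero.

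**Replacement is allowed** (protocol Section 5.2), but for premature discontinuation, not for one missed sample.

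**Conclusion.** The point holds. Followed as written, the plan can remove participants from both models for RNA samples the models never use, and from Table 5.1 for Part 1 doses given after the last RNA sample it uses. The expected loss due only to later samples is about 1.7 to 2.5 of 30 under Section 4, given independent missingness at an assumed 3% to 5%. It is zero if PP equals ITT. The direction of any bias is unknown.

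Three stronger readings are tempting but not supported:

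- A reader might take the whole PP shortfall as the harm: 12 × (1 − q⁸) + 18 × (1 − q⁶), or about 6 to 9 of 30 at 3% to 5%. Most of that comes from samples missed inside the Day 8 window, where exclusion rests on data the models do use.
- A reader might extend the missed-dose point to Table 6.1. A dose missed on Days 8 to 10 can change the Visit 5 exposure in that model, so excluding for it can be legitimate.
- A reader might express the precision loss through one arm mean, √(6/5) = 1.095, or about 10%. The model pools all doses, so the relevant figure is the 5% to 8% for ED50 in the working, under its assumed parameters.

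**What to change.** 1. For Table 5.1, define the model set by RNA scheduled on or before Day 8 and the doses preceding those samples. State how Part 1 participants whose Visit 5 falls on Day 9 or 10 are handled.
2. For Table 6.1, use the same RNA rule, and require doses through the Visit 5 PK profile and evaluable PK.
3. Add an ITT-Exposed fit of each model alongside (for Table 6.1, with evaluable PK), consistent with the protocol's use of both sets for efficacy analyses.
4. Make SAP Section 4 and Appendix 1 state one PP rule. Doing only this would leave the Part 1 Day 11 problem in place.

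The cost is SAP wording, entries in the display list, and rerunning the same code on differently selected records. No new data are needed.

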10.1.4. Statistical Analyses / Methods

Details of the planned displays are provided in [Appendix 11](#): List of Data Displays and will be based on GSK Data Standards and statistical principles.

Unless otherwise specified, endpoints / variables defined in Section [10.1.1](#) will be summarised using descriptive statistics, graphically presented (where appropriate) and listed.

Descriptive Summary tables are separated for Part 1 and Part 2 while the summary table for statistical modelling results are combined for two Parts.

In endpoint descriptive summary tables, the maximum change from baseline includes all visits while in model fitting it only includes visits from baseline to Day 8 in HIV-1 RNA for both parts.

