In the shortest course for Part 1, a participant can be screened/qualified, treated and assessed for all the planned visits (including the final follow-up visit) in approximately 30 days (if, for example, only 10-14 days are needed for the screening period and the final follow-up visit is performed on Day 18). In the longest course for Part 1, a participant can be screened/qualified, treated and assessed for all the planned visits (including the final follow-up visit) in 52 days (if, for example, 28 days are needed for the screening period and the final follow-up visit is performed on Day 24).

Study Part 2:

There are 2 in-clinic visits in the Part 2 post-dosing period: 1 visit for PK and other assessments on the day immediately following the last dose, and a final follow-up visit primarily for safety (e.g., to follow any AEs to resolution) 3-5 days after the last dose, as shown in the Part 2 Schedule of Activities (SOA, Section 2).

In Part 2, participants will start Investigator-selected, prescribed and provided cART immediately following the completion of the primary endpoint, i.e., the measurement of HIV-1 RNA on Day 8.

In the shortest course for Part 2, a participant can be screened/qualified, treated and assessed for all the planned visits (including the final follow up visit) in approximately 24 days (if, for example, only 10-14 days are needed for the screening period and the final follow-up visit is performed on Day 10). In the longest course, a participant can be screened/qualified, treated and assessed for all the planned visits (including the final follow-up visit) in 40 days (if, for example, 28 days are needed for the screening period and the final follow-up visit is performed on Day 12).

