3.2.4. Justification for Part 2 Treatment Duration and Initiation of cART

Data from Part 1 showed a decline in HIV-1 RNA and reasonable PK profile. There were no clinically significant trends in AEs, vital signs, ECG findings, or chemistry or haematology laboratory abnormalities across dosing arms. However, some participants receiving GSK3640254 had treatment emergent resistance mutations associated with maturation inhibitors observed on Day 11 (after 10 days of receiving GSK3640254 monotherapy). Additionally, no resistance to existing and commercially available classes of antiretroviral medications (e.g., reverse transcriptase, protease, integrase) was observed at Day 11 as there is no known cross-resistance between maturation inhibitors and other classes of ARVs. Genotypic analysis of samples at Clinic Visit 5 (Study Day 8 or 9) revealed no treatment emergent resistance. As a result, VH made two substantial changes to decrease the risk of treatment emergent resistance to participants in study Part 2: 1) decrease the duration of monotherapy from 10 days to 7 days (based on the interim genotypic analysis), and 2) immediately start Investigator-selected cART at the completion of monotherapy at the Part 2 primary endpoint (HIV-1 RNA measured on Day 8).

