4. OBJECTIVES AND ENDPOINTS

Objectives	Endpoints
Primary	

 To evaluate the antiviral activity of GSK3640254 in HIV-1-infected participants during 10 days of monotherapy in Part 1 and during 7 days of monotherapy in Part 2 	
 Maximum change from baseline (Day 1) in plasma HIV-1 RNA
Secondary	

 To assess the safety and tolerability of GSK3640254 when administered as monotherapy over 10 days in Part 1 and over 7 days in Part 2 in HIV-1 infected participants 	
 GSK3640254 safety and tolerability parameters: adverse events (AE); post-baseline values and changes over time of clinical laboratory evaluations, vital signs, and electrocardiogram (ECG) parameters

 To characterize the pharmacokinetics of GSK3640254 dosing for 10 days in Part 1 and for 7 days in Part 2 in HIV-1 infected patients 	
 GSK3640254 PK parameters at the following dose administration: Day 1: area under the plasma concentration time curve from zero to 24 (AUC [0-24]), maximum observed concentration (C_{max}), time to maximum observed concentration (t_{max}), concentration at 24 hours post dose (C₂₄), absorption lag time (t_{lag}) Following repeat administration: Area under the plasma drug concentration-time curve from pre-dose to the end of the dosing interval at steady state (AUC[0-τ]), C_{max}, t_{max}, pre-dose concentration (C₀), concentration at end of dosing interval (C_τ), apparent terminal phase half-life (t_{1/2}), and apparent oral clearance (CL/F), if data permit.

Objectives	Endpoints

 To explore the relationship between GSK3640254 exposure and change in plasma HIV-1 RNA 	
 GSK3640254 repeat-dose PK parameters AUC(0-τ), C_{max}, C_{τ} with maximum HIV-1 RNA change from baseline

 To estimate GSK3640254 accumulation following administration of GSK3640254 for 10 days in Part 1 and for 7 days in Part 2 in HIV-1 infected patients. 	
 Accumulation: GSK3640254 PK accumulation ratios (R): repeat -dose AUC (0-τ), C_{max}, and C_{τ} compared to Day 1 AUC (0-24), C_{max}, C₂₄, respectively

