7.8. Treatment and Care after the End of the Study

Given the lack of longer term clinical benefit (Section 3.3.2), VH recognizes the balance between the need to conduct an early phase monotherapy clinical trial (for the larger and long term unmet medical need) and the need for HIV-1 infected treatment naïve patients to receive cART as soon as possible after diagnosis. To meet both needs, this trial design is efficient in screening (shortest period: 14 days) and treatment/follow-up (shortest period: 18 days in study Part 1 and 10 days in study Part 2). A clinical trial commitment of as short as ~1 month is expected. After this time, VH expects all participating patients to receive local standard of care cART.

VH recognizes some HIV-1 infected adults may encounter barriers to accessing cART. Where it has been determined by the Investigator to be an acceptable option, participants receiving study treatment will have the option (but are not required) to receive reimbursement from the Sponsor for locally marketed ARVs (after the completion of dosing and through the study final follow-up visit) for up to a maximum of 90 days. The selection of ARVs will be investigator-chosen based upon local standard of care.

The investigator is responsible for ensuring that participants will be referred for prompt cART initiation after completion of the study, whether or not VH is providing reimbursement for post-study treatment.

In the case of Part 2, participants will start Investigator selected, prescribed and provided cART immediately after the completion of the primary endpoint; i.e., specifically to be administered in the clinic on Day 8 after the blood collection has been performed.

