10. STATISTICAL CONSIDERATIONS

10.1. Sample Size Determination

10.1.1. Sample Size Considerations

The primary objectives of this study are to investigate the safety, tolerability and antiviral activity of GSK3640254 over a 10-day treatment period in study Part 1 and over a 7-day treatment period in study Part 2. The antiviral activity will be assessed by estimating plasma HIV-1 RNA max change from baseline during the study.

The sample size for this study is based primarily on feasibility to provide adequate precision for the estimations.

Based on data from the short-term monotherapy study of BMS-955176/GSK3532795 POC (AI468002) study and GSK2838232 POC study, we assumed the maximum change from baseline viral load drop (VLD) values on log scale for individual participants from the higher dose in Part 1 follow a normal distribution. Therefore, we conducted 1000 trial

simulations in Fixed and Adaptive Clinical Trial Simulation (*FACTS*) software using the normal distribution with mean of change from baseline VLD on log scale at 0.5 to 2 copies, SD=0.4, and sample sizes=6 for Part 1 higher dose.

Using Bayesian calculation with non-informative priors for the mean and weakly informative priors for the error parameters, Normal (0, 100) for mean and Inverse Gamma (0.35, 0.0875) for error parameters, the posterior probability to achieve a clinically relevant cut-point of 1.3 log was calculated for each simulated trial, and percentage of the trials with posterior probability of mean viral load drop (VLD) at the higher dose in Part 1 >1.3 log (given the true mean VLD on log scale) $\geq 20\%$ was calculated and are shown below in [Table 5](#).

Table 5 Percentage of the trials with posterior probability $\geq 20\%$ for Part 1 higher dose using sample size=6

True Mean VLD on log scale	Posterior Probability $\geq 20\%$	Posterior Probability $< 20\%$
0.5	0.0%	100.0%
0.7	0.1%	99.9%
0.8	0.6%	99.4%
0.9	4.6%	95.4%
1	15.0%	85.0%
1.1	35.9%	64.1%
1.2	60.8%	39.2%
1.3	81.8%	18.2%
1.4	92.4%	7.6%
1.5	97.9%	2.1%
1.6	99.8%	0.2%
1.7	100.0%	0.0%
2	100.0%	0.0%

The precision of the dose response curve (with sample size N=6) is provided in [Table 1](#) (Section [5.5.1](#)).

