7.1. Primary Efficacy Analyses

7.1.1. Endpoint / Variables

- Change from baseline to the nadir (maximum change from baseline) in Plasma HIV-1 RNA
- Change from baseline to Visit 6 (Day 11 in Part 1 and Day 8 in Part 2) in Plasma HIV-1 RNA

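### The Part 2 primary nadir has no Day 8 cut-off, so HIV-1 RNA measured after cART has started can set the maximum change from baseline

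*SAP*

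**What the plan says.** The primary objective in Protocol Section 4 is antiviral activity "during 10 days of monotherapy in Part 1 and during 7 days of monotherapy in Part 2", and the only endpoint set against it is maximum change from baseline in plasma HIV-1 RNA. The Synopsis has Part 2 participants start "cART immediately following the completion of the primary endpoint, i.e., the measurement of HIV-1 RNA on Day 8". Section 3.2.4 says the same, and Section 7.8 specifies that cART is "to be administered in the clinic on Day 8 after the blood collection has been performed".

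The statistical text does not carry that boundary over:

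- Protocol 10.1.1: "The antiviral activity will be assessed by estimating plasma HIV-1 RNA max change from baseline during the study".
- Protocol 10.3.2.2: "Plasma HIV-1 RNA max change and change from baseline during the study will be calculated for each participant".
- SAP 7.1.1 lists "Change from baseline to the nadir (maximum change from baseline) in Plasma HIV-1 RNA" as a primary variable, with no last visit. The second variable there, change to Visit 6, is fixed at Day 8 in Part 2.
- SAP 10.1.4, on descriptive tables: "the maximum change from baseline includes all visits while in model fitting it only includes visits from baseline to Day 8".

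The Part 2 Schedule of Activities draws HIV-1 RNA at Visit 7, and SAP 13.3.1 gives that visit an efficacy window opening on Day 10. No rule removes values taken after cART begins. SAP 13.5.2 drops only unscheduled visits from tables, and Visit 7 is scheduled. SAP 2.1 reports no departure from the protocol's planned analysis.

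**The concern.** A sample taken on cART cannot measure monotherapy activity. If it may serve as the nadir, the headline result for 40, 80 and 140 mg becomes a mixture of GSK3640254 and an investigator-chosen regimen.

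The bias runs towards larger declines in every arm that starts cART. The two Part 2 placebo participants would appear to respond, and the contrast between active and placebo would be distorted. Time to nadir would move past the end of dosing. Part 1 participants take no ARVs before final follow-up, so the same statistic would mean different things in the two parts. Table 2.4 would also show a nadir and a Day 8 change side by side that differ partly because of cART.

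**Working it through.** **Timing.** The last Part 2 dose is on Day 7 and final follow-up is 3 to 5 days later: 7 + 3 = Day 10 to 7 + 5 = Day 12. cART starts on Day 8, so Visit 7 falls 10 − 8 = 2 to 12 − 8 = 4 days into cART.

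**Displays reached.** Section 10 of the SAP has one table of its own, the dose-response model (Table 5.1). The descriptive maximum-change tables split by part are in the efficacy set. For Part 2 these are Tables 2.4 (ITT) and 2.20 (PP), with time to nadir in 2.6 and 2.22. The mixed model of the nadir in SAP 7.1.3.1 (Tables 2.8 and 2.24) states no window and may be affected. The Visit 6 change and the Section 10 and 11 models stop at Day 8.

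**Scale.** The plan gives no figure for the effect of Visit 7. Its only design figure is Protocol Table 5, which concerns Part 1 and does not bear on this point. Under its normal model (SD 0.4, n = 6, inverse gamma (0.35, 0.0875) error prior, near-flat mean prior), the posterior of the mean is Student t with 6 − 1 + 2 × 0.35 = 5.7 degrees of freedom. At a true mean of 1.3 the recalculation gives 81.2%, against 81.8% stated. Two of the 11 rows checked differ by more than 2 points (true means 0.9 and 1.0), which is not treated as an error. The planning standard error of an arm mean is 0.4/√6 = 0.163 log10.

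**Size, first set of assumptions.** Part 2 participants were simulated in 96 scenarios:

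- samples on Day 2, 3–4, 5–6, 7, 8 and 10–12
- linear decline to Day 8 with mean 0, 0.8, 1.0 or 1.5 log10 (between-participant SD 0.4 when non-zero, truncated at 0)
- after Day 8, a further fall of 0.1, 0.2, 0.35 or 0.5 log10 per day (assumed)
- measurement SD 0.1 or 0.2 (assumed)
- baseline 5,000, 30,000 or 100,000 copies/mL (assumed)
- values below 50 set to 49 copies/mL (SAP Section 7)

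For each participant the largest decline through Day 8 was compared with the largest over all visits.

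| True mean decline at Day 8 | Mean maximum decline, through Day 8 | Mean maximum decline, all visits |
|---|---|---|
| 0 | 0.12–0.23 | 0.31–1.50 |
| 0.8 | 0.83–0.89 | 1.10–2.30 |
| 1.5 | 1.48–1.54 | 1.72–2.89 |

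Across scenarios the all-visits rule deepens the mean nadir by 0.14 to 1.47 log10, and by 0.14 to 0.30 at the slowest slope. Visit 7 is the nadir in about 60 to 100% of participants. In active arms the mean time to nadir moves from Day 7.2–7.9 to Day 10.2–11.0. At a true decline of 1.0, roughly 41 to 81% of the reported nadir is earned by Day 8. From a baseline of 5,000 copies/mL the largest recordable decline is log10(5000/49) = 2.01, which caps the excess there.

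**Size, second set of assumptions.** Between-participant SD 0.35 and within-participant SD 0.2 give a total of √(0.35² + 0.2²) = 0.40. A fixed extra fall by Visit 7 was then added:

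| Extra fall by Visit 7 | True 1.0: through Day 8 → all visits | Nadir at Visit 7 | True 0: through Day 8 → all visits | Nadir at Visit 7 |
|---|---|---|---|---|
| 0.2 | 1.07 → 1.25 | 70% | 0.27 → 0.35 | 42% |
| 0.5 | 1.07 → 1.50 | 95% | 0.27 → 0.54 | 79% |
| 0.8 | 1.07 → 1.80 | over 99% | 0.27 → 0.81 | 96% |
| 1.0 | 1.07 → 2.00 | over 99% | 0.27 → 1.00 | 99% |

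With no further fall at all, one extra noisy sample deepens the nadir by only 0.02 to 0.09 log10.

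**The case against.** **The all-visits sentence sits in the pharmacodynamic section, and its other half limits model fitting to Day 8.** If it governs Section 7, that limit might protect the nadir mixed model too; if it does not, Section 7 is merely silent and the protocol narrative implies Day 8. The first half most naturally describes the efficacy tables, since Section 10 lists no descriptive table. The Day 8 limit fits the Section 7 model poorly, because that model uses Day 11 in Part 1. The status of Tables 2.8 and 2.24 therefore remains open.

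**The narrative itself calls the Day 8 measurement the Part 2 primary endpoint.** That stands: these passages need reconciling. It also supports ending the nadir at Day 8, and the objectives table still names only maximum change.

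**Little inference depends on it.** No hypotheses are tested, the Go/No Go rule uses Part 1 only, and the dose-response and exposure-response models stop at Day 8. Time to nadir and by-visit RNA would expose an on-cART nadir. This limits the damage but does not correct the reported primary endpoint.

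**The size is assumed.** This stands. The slopes were chosen, with no lag after the first cART dose. The slowest, 0.1 log10 per day, is below the on-drug slope of 1.0/7 = 0.14 per day. With a half-life of about 22 to 29 hours, part of the low-end excess in active arms could be residual drug.

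**The fix does not make Part 2 fully comparable with Part 1.** True: Part 1 would still have 10 days of dosing and a nadir that can fall after dosing ends.

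**Conclusion.** The concern holds. As written, the plan lets an on-cART sample set the Part 2 nadir and time to nadir in Tables 2.4, 2.6, 2.20 and 2.22, contrary to the 7-day monotherapy objective and the protocol's own statement that the endpoint is complete at Day 8. Tables 2.8 and 2.24 may be affected.

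The documents alone establish the direction of the bias. Its size depends on the assumed fall after Day 8: 0.14 to 1.47 log10 under the first set of assumptions, and 0.18 to 0.93 for a true decline of 1.0 under the second. Even the slow end is close to or above one planning standard error. Because this is the protocol's named primary endpoint, it should be corrected before the final analysis.

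**What to change.** In SAP 7.1.1, 7.1.3.1 and 10.1.4, define the Part 2 nadir and time to nadir over post-baseline HIV-1 RNA up to and including the pre-cART Visit 6 (Day 8) sample, and exclude any sample taken after the first cART dose. Apply this to Tables 2.4, 2.6, 2.8, 2.20, 2.22 and 2.24. Show Visit 7 RNA in by-visit displays only, labelled as on cART. Record the change in SAP 2.1 as a clarification of the protocol's open-ended wording. The Part 1 nadir can stay as it is, with a note that the two parts cover different periods.

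The cost is SAP wording and one derivation flag, with no new data and no change to participant management. Reported Part 2 maximum declines will be smaller. Any further fall after Day 8 from residual drug will not be counted, but it cannot be separated from cART in any case.
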